5.0 Inclusion and Exclusion Criteria/ Study Population

Patients who are diagnosed with presbyphonia and who have already sought and begun voice care at MUSC, will undergo a brief screening interview by [name], after which qualifying patients will be offered participation in the study. A study team member will meet with interested participants and will provide a thorough description of the study prior to obtaining formal written consent. Participants who don't meet stratification requirements will be excluded from the study.

Inclusion Criteria

The participant:

- must receive a diagnosis of presbyphonia by a trained laryngologist. The
 diagnosis will be given following a visual examination of the larynx if the
 observations are consistent with the characteristics of a presbylarynx, as
 judged by the laryngologist.
- must have already undertaken their voice care at MUSC
- must be 50 years and older
- must be English-speaking
- must sign the informed consent

Exclusion Criteria

The participant

- has received voice therapy in the past year (other than current care)
- presents with a vocal fold pathology other than presbyphonia
- has a known neurologic or a progressive neuromuscular disease
- doesn't meet the stratification requirements for muscle pressure
- has a medical condition that could be aggravated by the experimental intervention, or any condition judged by the physician ([name]) as being unsuitable for respiratory training.
- has dysarthria or a language disorder
- has a hearing loss that is not adequately managed
- has a cognitive disorder that might affect treatment compliance
- is unable to give informed consent

Inclusion of Women

No subjects will be excluded based on gender. Based on published literature, treatment seeking patients with presbyphonia are generally equally divided between female and male. Thus, we estimate that approximately 50% of study participants will be female. No outreach program to recruit women is planned, because all patients with presbyphonia who meet inclusion criteria after undergoing a voice evaluation at the participating institution, regardless of gender, will be invited to participate. While no subjects will be excluded based on gender, it is highly likely that the majority of participant raters will be women as that is the current composition of speech-language pathologists.

Inclusion of Minorities

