12.0 Data Management

Data Analysis Plan

Demographic characteristics will be compared across the 3 intervention groups, using a RxC contingency table method for categorical variables (gender, smoking history, voice use, racial and ethnic category) and a one-way ANOVA for continuous variables (age, weight, height). Baseline characteristics will be compared across the 3 intervention groups using a Kruskal-Wallis one-way analysis of variance by ranks for ordinal data (GFI, RSI, and VHI scores), a RxC contingency table for categorical variables (glottal gap shape, free edge contour, vertical level, phase closure) and a one-way ANOVA for continuous variables. Aim 1: To assess the effects of respiratory training on voice and respiratory outcomes in patients with presbyphonia. Data will be analyzed on an intention-to-treat basis using multifactor repeated measures generalized linear regression. Distributional assessment will be made for each outcome to confirm optimal distributional assignment and potential need for outcome transformation (i.e. log link). In the model, the repeated factor is time, which has two levels (pre- or post-intervention) and the independent factor is the intervention, which has three levels (IMST, EMST, VFE). In the case of a significant between-subjects effect, multiple comparison tests will be conducted to determine which groups differ. The post-hoc analysis will be done using Tukey's honestly significant difference (offering protection against type I error without being too conservative). Spearman and Person correlations will be calculated to establish inter and intrarater reliability. Aim 2: To identify profiles of presbyphonic patients that would benefit the most from respiratory training. Logistic regression will be conducted to predict which patients improved following inspiratory training and which patients improved following expiratory training, based on their baseline clinical characteristics. Two outcome variables will be indicative of meaningful clinical improvement: 1) MPT (to measure function), and 2) GFI (to measure patient perception of function). Meaningful clinical improvement will be defined by an increase of at least 4 seconds in MPT or a decrease of at least 4 points in GFI score. Participants will be dichotomized as having meaningful clinical improvement, or not, based on these outcomes. Predictors will include MIP, MEP, maximum SPL, breaths per minute, FVC, FEV1, and P_s. These measures were chosen because they are directly influenced by the integrity of the respiratory system.

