
Sample Size Justification

We considered maximum phonation time (MPT) as the primary outcome measure for sample size calculation. This measure was chosen because 1) low MPT is a hallmark of patients with presbyphonia, and 2) MPT is directly affected by both the laryngeal and respiratory systems. To estimate the expected effect size between VFE and the I+IVFE and E+VFE groups, we considered MPT values from groups of an

elderly population with different glottal closure and spirometry profiles (49). Considering that a combined intervention (inspiratory or expiratory training combined with voice therapy) would address both laryngeal and respiratory deficits, and that a voice therapy-only intervention would directly address only the laryngeal deficits, we compared MPT between the no-deficit group (complete glottal closure and normal spirometry) and the respiratory-deficit group (complete glottal closure and altered spirometry)(49). Based on these values and the pooled standard deviations, the expected difference between our control and experimental groups would represent a large effect size. As for the withinsubjects effect, a study by Nam et al.(50) found a 33% increase in MPT following a respiratory training intervention program in young adult singers. This corresponds to a very large within-subjects effect size with values of d exceeding 1.2. For Aim 2, we will assess improvement in 2 ways: function (a MPT increase of 4 seconds, which has been associated with a positive perceived effect following voice therapy in older adults(51)) and patient perception of function (a Glottal Function Index (GFI) score decrease of 4 points). An increase of 4 seconds in MPT and a decrease of 4 points on the GFI instrument both correspond to medium-large effect sizes considering the reported standard deviations of these measures in older subjects and in patients with glottal insufficiency (5.1 and 4.5, respectively) (42, 52). Based on the reported studies, the expected effect size for within-subjects and between-subjects differences was set at d=0.90. To have an 80% power to detect an effect size of d=0.90 with an alpha of 0.1 (since this is a pilot study), 15 participants are needed in each group. To account for loss to follow-up (estimated 10% dropouts rate), up to 16 participants will be recruited for each group, 48 patients total.

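### Aim 2 defines response by fixed MPT and GFI cut-offs and does not name starting MPT or GFI as predictors, so a respiratory-profile association can partly reflect where patients started

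*Combined protocol and SAP*

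**What the plan says.** Section 12.0, Data Analysis Plan, Aim 2, defines meaningful improvement as "an increase of at least 4 seconds in MPT or a decrease of at least 4 points in GFI score" and continues: "Participants will be dichotomized as having meaningful clinical improvement, or not, based on these outcomes". Logistic regression is used to find which patients improved after inspiratory training and which after expiratory training. No contrast with the voice-exercise (VFE) arm is described.

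The predictor list reads "Predictors will include MIP, MEP, maximum SPL, breaths per minute, FVC, FEV1, and P_s". The reason given is: "These measures were chosen because they are directly influenced by the integrity of the respiratory system". Baseline MPT and baseline GFI are not named. Baseline GFI appears in the same section only in a comparison of the three arms.

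On entry, section 5.0 says that the participant "must receive a diagnosis of presbyphonia by a trained laryngologist". The only measurement-based rule there concerns the muscle-pressure strata, and the stratification in section 10.0 uses MIP and MEP only.

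The Sample Size Justification in section 12.0 says that "low MPT is a hallmark of patients with presbyphonia" and that MPT depends on the lungs as well as the larynx. It also cites a study that "found a 33% increase in MPT following a respiratory training intervention program"; the subjects of that study were young singers.

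**The concern.** A fixed absolute cut is not equally easy to reach from every starting point. If gains grow with the starting value, patients who begin with a long MPT cross 4 s more easily. If they do not, measurement error makes patients who begin low appear to gain more. On the GFI, a patient who starts below 4 cannot fall by 4 points (taking 0 as the lowest score, which the documents do not state).

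Starting level matters for the profile question only if it is related to the predictors. For MPT the plan supplies that link: it describes both MPT and the predictors as depending on the respiratory system. A baseline that drives response, is related to the predictors and is left out of the model will show up as a predictor effect. Randomisation and stratification do not prevent this, because the comparison is between patients within a trained arm.

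At stake are the two Aim 2 hypotheses in section 1.0: that inspiratory training works best when MIP is decreased, and expiratory training when MEP is decreased. The plan intends the resulting profiles to guide which patients receive which training.

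**Working it through.** **The plan's own figures.** The Sample Size Justification gives SDs of 5.1 s (MPT) and 4.5 points (GFI). 4/5.1 = 0.78 and 4/4.5 = 0.89, which agrees with its description of the cut-offs as medium to large effects. Aim 2 has no power figure of its own.

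**Dependence on starting MPT if gains are proportional.** Using the cited 33%, a 4 s gain needs a baseline of 4/0.33 = 12.1 s. From 9 s, the gain is 9 × 0.33 = 3.0 s (not a responder). From 15 s, it is 15 × 0.33 = 5.0 s (responder). With a normal distribution and SD 5.1, the share starting below 12.1 s is Φ((12.1 − mean)/5.1). That is 79%, 66%, 51% or 29% for assumed means of 8, 10, 12 or 15 s.

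**Dependence in the other direction, from measurement error.** Take no treatment effect and test-retest correlation r (assumed). For a patient k SDs from the mean at baseline, change has mean (r − 1)·k·5.1 and SD 5.1·√(1 − r²). At r = 0.8 the SD is 5.1 × 0.6 = 3.06.
- One SD below the mean: 1 − Φ((4 − 1.02)/3.06) = 16.5% gain at least 4 s.
- One SD above the mean: 1 − Φ((4 + 1.02)/3.06) = 5%.

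Over r = 0.7 to 0.9 the ranges are 25% to 6% for low starters and 6% to 2% for high starters.

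**Effect on the MIP association.** This was simulated with the same median 33% gain for every patient and no MIP effect on the proportional gain. From the plan: SD 5.1 s. Assumed: log-normal baseline MPT with mean 10 to 15 s, MIP–MPT correlation 0.3 to 0.5, and SD of the log gain 0.15.

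| Reliability of MPT (assumed) | Odds ratio for response, MIP above vs below median |
|---|---|
| 1.0 | 1.41 to 2.47 |
| 0.8 | 1.22 to 1.69 |

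An example at reliability 1.0, mean 12 s and correlation 0.5: response is 33.5% (low MIP) and 51.8% (high MIP), so the odds ratio is (0.518/0.482)/(0.335/0.665) = 2.1. With log-gain SD 0.25, mean 15 s and correlation 0.3, it is 1.25. A similar simulation with FVC gave odds ratios per SD of 1.26 to 1.76 without baseline MPT. At zero correlation between predictor and baseline it gave 1.00.

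**Does adding baseline to the logistic model cure it?** With error-free MPT, yes: the odds ratio per SD of MIP returns to 0.99–1.01. At reliability 0.8, no: 1.13 to 1.32 per SD remains within an arm, because measured baseline only partly captures true baseline. The model is also too small. Sixteen per arm gives at most 16/2 = 8 patients in the smaller outcome class. That is 8/7 = 1.14 events per predictor now, and 8/8 = 1.0 with one baseline added.

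**GFI.** With SD 4.5, whole-number scores and a floor of 0 (the last two assumed), the share starting below 4 is Φ((3.5 − mean)/4.5). That is 29%, 16%, 7% or 3% for assumed means of 6, 8, 10 or 12. These patients cannot respond on GFI. This becomes a profile effect only if GFI is correlated with the predictors, which the documents do not say.

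**The case against.** The strongest reply is that the 4 s cut is deliberate. The plan ties it to a perceived benefit in older adults, and Aim 2 is worded as prediction of who improved. On that reading, a patient who goes from 9 s to 12 s is rightly a non-responder, and a longer-MPT patient who gains more seconds really did improve more. This stands as a reason to keep the cut as a description. It does not answer the hypotheses in section 1.0, which concern where training has most effect. An unadjusted association within a trained arm cannot separate that from starting level.

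Three further points stand in part:
- The wording of the predictor list is not exclusive and would permit baseline MPT or GFI. Neither is named, however, and the stated reason for selection covers respiratory measures.
- It is unclear whether MPT and GFI are to be two outcomes or one either/or outcome. As a composite, a patient who fails on one measure can qualify on the other, which dilutes the MPT effect: with an assumed independent GFI response, the odds ratio of 2.1 falls to about 1.7.
- With 16 per arm, the standard error of a log odds ratio from a median split is about 1.0, so sampling noise exceeds this bias and a spurious significant result would be uncommon. The estimates would still be read as profiles.

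A reader might infer that the analysis will show the reverse of the plan's hypothesis. The documents do not support that. The 33% comes from young singers and is cited only for a within-subject effect size. No MIP–MPT correlation is given, and regression to the mean pulls the other way.

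**Conclusion.** The concern holds for MPT as a problem of interpretation. As written, Aim 2 cannot distinguish a respiratory-profile effect from a starting-MPT effect. The fixed cuts, the absence of an MPT or GFI entry limit, and the absence of both baselines from the named predictors are all in the text.

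The size is conditional. An odds ratio of about 1.2 to 2.5 for high versus low MIP requires a uniform 33% median gain, log-gain SD 0.15, and the assumed baseline means, correlations and reliability. The upper end needs MPT measured without error. The direction is not established.

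Two stronger readings should be resisted. One is that GFI is equally affected: the documents link MPT, but not GFI, to respiratory function. The other is that the 4 s and 4-point cuts are wrong as markers of clinical improvement: nothing here shows that. The point concerns Aim 2 only and leaves the sample size unchanged.

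**What to change.** For the MIP and MEP hypotheses, make the main Aim 2 analysis a model of final MPT (log scale if the distributional check already planned supports it) and, separately, of final GFI, each adjusted for its own baseline. Use all three arms, with an arm-by-baseline-MIP interaction for inspiratory training against VFE and an arm-by-baseline-MEP interaction for expiratory training against VFE. Enter only the hypothesised predictor, not all seven.

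The VFE contrast is needed because baseline adjustment within one arm leaves a residue when MPT is measured with error. On the log scale, if each arm shifts log MPT by a constant, that residue is the same in every arm and cancels in the interaction. Interactions depend on the scale, so the scale should be settled before the interaction is examined.

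Keep the 4 s and 4-point responder splits as descriptive results, reported separately for MPT and GFI, and state how many participants start with GFI below 4.

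The cost is analysis wording only, since both baselines are already needed to compute the changes. The downside is precision: at 16 per arm the interaction estimate will be wide. It should be reported as exploratory with a confidence interval.

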Specific Aim 1: To measure the effects of respiratory training on respiratory and voice outcomes in patients with presbyphonia. Hypothesis 1: The respiratory training groups (inspiratory and/or expiratory) will demonstrate greater improvement in respiratory outcomes, measured through pulmonary function tests and respiratory pressure measures, compared with the voice exercises-only group. Hypothesis 2: The respiratory training groups (inspiratory and/or expiratory) will demonstrate greater improvement in voice-related outcomes than the voice exercises-only group.

Secondary Aim 1: To assess the reliability of the ratings for subjective outcomes (videostroboscopy ratings and perceptual judgements of voice quality). Hypothesis 1: Intra-judge reliability will be of at least 80%. Hypothesis 2: Inter-judge reliability will be of at least 70%.

Specific Aim 2: To determine how baseline measures of respiratory function influence the effects of respiratory training (respiratory and voice outcomes). Hypothesis 1: inspiratory training will have maximal effect on patients with decreased maximum inspiratory pressure (MIP). Hypothesis 2: Expiratory will have maximal effect on patients with decreased maximum expiratory pressure (MEP).

This is an initial feasibility and mechanistic study that has the potential to reveal that respiratory training can significantly improve outcomes from voice therapy by acting in synergy with voice exercises. Currently,

much time is spent in voice therapy on subthreshold 'breathing exercises' that lack evidence. This project will provide guidance for evidence-based and theory driven approaches to leverage respiratory function to improve voice therapy. Conversely, negative findings from this study would indicate that respiratory function is ineffective and not a viable target for therapy in this patient population.

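### Aim 2 cuts MPT and GFI change to improved/not improved before testing baseline predictors, which discards information with about 15 patients per trained arm; the size of the loss is conditional

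*Combined protocol and SAP*

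**What the plan says.** The Data Analysis Plan (section 12.0) sets the Aim 2 criterion as follows: "Meaningful clinical improvement will be defined by an increase of at least 4 seconds in MPT or a decrease of at least 4 points in" the GFI score. It continues: "Participants will be dichotomized as having meaningful clinical improvement, or not, based on these outcomes". The model is then given: "Logistic regression will be conducted to predict which patients improved following inspiratory training and which patients improved following expiratory training". Seven baseline measures enter: "Predictors will include MIP, MEP, maximum SPL, breaths per minute, FVC, FEV1, and P_s".

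Section 1.0 frames the aim as a question of degree: "To determine how baseline measures of respiratory function influence the effects of respiratory training (respiratory and voice outcomes"). Its two hypotheses expect the largest effect of inspiratory training where MIP is low and of expiratory training where MEP is low.

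The Sample Size Justification gives the reason for the MPT threshold: "a MPT increase of 4 seconds, which has been associated with a positive perceived effect following voice therapy in older adults". It describes MPT and GFI as two ways of judging improvement. It states no power for the Aim 2 regressions. The Aim 1 model contains only time and intervention, so no other planned analysis relates measured change to baseline respiratory function.

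**The concern.** Whether low MIP or MEP goes with a larger gain is a question about the size of change, and the planned outcome no longer carries size. With a separate MPT cut, a gain of 3.9 s is coded like a loss, and a gain of 4 s like a gain of 12 s. With roughly 15 patients in each trained arm there is little information to spare.

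Aim 2 is meant to guide which type of training a patient receives. The stake is that a real dependence of benefit on MIP or MEP is missed. There is a second cost. At this sample size the logistic likelihood-ratio test rejects more often than its nominal level, so part of its apparent power is false positives.

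**Working it through.** **The plan's own sample size.** The plan states: "To have an 80% power to detect an effect size of d=0.90 with an alpha of 0.1 (since this is a pilot study), 15 participants" per group. Normal formula: n = 2 × ((1.645 + 0.842) / 0.90)² = 15.3, so 16 after rounding up. The exact t calculation gives 15.99. At n = 15 the t-test power is 77.6%. The stated figure is therefore reproduced to within one patient. It concerns a two-group comparison, not Aim 2. With 16 recruited and 10% dropout, 16 × 0.9 = 14.4 per arm are expected to finish, so n = 15 is used below.

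**Inputs from the documents.** Cuts of 4 s and 4 points; alpha 0.10 (stated for the d = 0.90 calculation); "reported standard deviations of these measures in older subjects and in patients with glottal insufficiency (5.1 and 4.5, respectively"). These are SDs of the measures, not of change.

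**Inputs assumed.**
- One standard normal predictor X, with change = mean + SD × (ρX + √(1 − ρ²)·e).
- ρ from 0.3 to 0.6.
- SD of change 5.1 s.
- The same alpha for Aim 2, two-sided.
- A likelihood-ratio test for the logistic model.

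**Share reaching 4 s.** P = 1 − Φ((4 − mean)/SD).
- Mean 4 s: 1 − Φ(0) = 50%.
- Mean 2 s: 1 − Φ(0.392) = 35%.
- Mean 0.9 × 5.1 = 4.59 s: 1 − Φ(−0.116) = 55%.

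**Separate MPT cut, n = 15** (simulation, 20,000 trials per cell; the full-scale test is the linear-regression t-test of the slope):

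| ρ | Full scale | Logistic, 50% improved | Loss | Loss at equal 10% error | Logistic, 35% improved | Loss | Loss at equal 10% error |
|---|---|---|---|---|---|---|---|
| 0.4 | 45% | 39% | 6.8 | 12.8 | 37% | 8.5 | 14.5 |
| 0.5 | 63% | 52% | 11.0 | 17.2 | 50% | 12.8 | 19.4 |
| 0.6 | 81% | 67% | 13.7 | 19.4 | 65% | 15.9 | 22.2 |

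With the mean gain of 4.59 s the nominal losses are 5.9, 11.3 and 13.6 points. At ρ = 0.3 the nominal loss is about 0-4 points (7-10 at equal error), and power is only about 30% even without the cut. Under the null the linear test rejects 10% and the logistic test 13-14%.

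Hand check of one cell (Fisher z, ρ = 0.5): atanh(0.5) × √12 = 0.549 × 3.464 = 1.903; 1.903 − 1.645 = 0.258; Φ(0.258) = 60%. This is close to the simulated 63%.

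**One composite responder** (MPT or GFI criterion met; mean gains of 4, SDs 5.1 and 4.5, the predictor assumed equally correlated with both changes, 4,000 trials):

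| ρ | MPT on full scale | Logistic on composite | Difference |
|---|---|---|---|
| 0.3 | 30% | 31% | −1 |
| 0.4 | 46% | 42% | 4 |
| 0.5 | 63% | 57% | 6 |
| 0.6 | 82% | 73% | 9 |

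Across the settings run, the nominal loss is about 2-9 points at ρ = 0.4-0.6. The composite test also rejects about 13-14% under the null.

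**All seven predictors in one model.** A linear fit leaves 15 − 8 = 7 residual degrees of freedom. With uncorrelated predictors, full-scale power falls to 30%, 41% and 58% at ρ = 0.4, 0.5 and 0.6. Logistic regression meets complete separation in about 73% of trials at n = 15 and 63% at n = 16 (ρ = 0.5, half improved), so its ordinary estimates are not finite.

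**The case against.** The cut has a stated clinical purpose. The Data Analysis Plan restates Aim 2 as finding the patient profiles that benefit most, and predicting who reaches a perceptible change is a legitimate responder question. A slope in seconds answers a different one. This supports reporting the proportions who reach 4 s and 4 points. It does not justify testing the section 1.0 hypotheses, which concern degree of effect, only on the cut outcome.

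The wording is also ambiguous. Read literally, the *or* makes one composite responder, and a patient with a 3.9 s gain still counts as improved if GFI falls by 4 points. The Sample Size Justification points to two outcomes. Under the composite the nominal loss is smaller and vanishes at a correlation of 0.3. This objection stands, and is why both readings are given.

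The inputs that drive the size are not in the documents, and the main figures use one predictor where the plan lists seven. That stands too: the figures are illustrations under stated assumptions. The unnamed choice of logistic test matters as well. A Wald test is conservative here (size about 4-6%) and would lose roughly 22-44 points at nominal alpha with 35-55% improved.

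Finally, this is a proof-of-concept study with no power claimed for Aim 2, which limits the severity.

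**Conclusion.** The concern holds in conditional form. Cutting the outcome discards information that Aim 2 needs, and nothing else in the plan recovers it. At n = 15, with one predictor, normal change, two-sided alpha 0.10, a likelihood-ratio test and about 35-50% reaching 4 s, a separate MPT cut costs about 6-16 points at correlations of 0.4-0.6 and 0-4 points at 0.3. Under the composite reading the cost is about 2-9 points and none at 0.3. Losses at equal type I error are larger, because the logistic test runs at about 13-14%.

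Three stronger readings are tempting and are not supported.
- A reader might infer a fixed, double-digit loss. The documents give no correlation, SD of change, share improved or alpha for Aim 2, and leave the responder definition open.
- A reader might infer that the full scale makes Aim 2 well powered. At moderate correlations it does not, and with seven predictors power drops further. The predictor count is a separate and larger problem.
- A reader might infer that Aim 1 already supplies the analysis. It keeps outcomes on their own scale but contains no baseline predictor.

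This is an avoidable efficiency loss in a secondary question, worth correcting before analysis. It does not undermine the trial.

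**What to change.** In section 12.0, Data Analysis Plan, Aim 2:
- Make the predictor analysis a regression on full-scale change, with one model for MPT change in seconds and one for GFI change in points (linear, or rank/ordinal if the distribution requires it).
- In each trained arm, test first the predictor named in the section 1.0 hypothesis: baseline MIP in the inspiratory arm and baseline MEP in the expiratory arm. Label the remaining predictors exploratory.
- Keep the proportions reaching 4 s on MPT and 4 points on GFI as a descriptive responder summary by arm.

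The cost is a rewording of one paragraph, with no new data, visits or patients. Effects will be reported in seconds or points instead of odds of improving, which the retained proportions partly offset. There will be two outcome models where the composite reading has one, so the plan should present them as two separate outcomes.

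### Aim 2 regresses a yes/no outcome on seven predictors in about 15 patients per training arm; read plainly, each model has no finite estimates half the time or more when no predictor matters

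*Combined protocol and SAP*

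**What the plan says.** Section 12.0, Data Analysis Plan, Aim 2: "Logistic regression will be conducted to predict which patients improved following inspiratory training and which patients improved following expiratory training". The outcome is binary. Improvement means "an increase of at least 4 seconds in MPT or a decrease of at least 4 points in GFI score", and "Participants will be dichotomized as having meaningful clinical improvement, or not, based on these outcomes". The covariates are listed in one sentence: "Predictors will include MIP, MEP, maximum SPL, breaths per minute, FVC, FEV1, and P_s".

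Section 12.0, Sample Size Justification: "15 participants are needed in each group", and after a dropout allowance ("estimated 10% dropouts rate"), "up to 16 participants will be recruited for each group, 48 patients total". That calculation rests on a standardised difference of 0.90. The section discusses the Aim 2 improvement thresholds but gives no power, event count or responder rate for the regression.

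Section 1.0 gives Aim 2 two hypotheses: inspiratory training works best where MIP is low, and expiratory training where MEP is low. It also promises to evaluate the interaction between type of training and baseline respiratory function.

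Nowhere do the documents mention variable selection, a penalised or exact method, validation, or what to do if the model does not converge.

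**The concern.** Each arm-specific model would have eight parameters (seven predictors plus an intercept) and at most 16 patients. At a 50% response the smaller outcome class holds at most 7 or 8 patients, so about one event per predictor at best. With so many dimensions per patient, some linear combination of the predictors often splits improvers from non-improvers perfectly by chance. The maximum-likelihood coefficients are then infinite, and the Wald tests and intervals mean nothing.

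Aim 2 is a named specific aim. Sections 2.0 and 16.0 say that its results should identify patient profiles and, once validated, inform who receives which training. A model that gives near-perfect apparent prediction from unrelated variables cannot serve that purpose. The two hypothesised predictors, MIP and MEP, would also compete with five others for very little information.

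**Working it through.** **The plan's own figure.** For d = 0.90, two-sided alpha 0.10 (sidedness is not stated) and 80% power, n per group = 2(1.645 + 0.842)² / 0.90² ≈ 15.3. This matches the stated 15 to within rounding; t-test power is 77.6% at 15 and 80.0% at 16. With 10% dropout, 16 × 0.9 = 14.4 completers. The relevant range is therefore 14 to 16 per arm. None of this sizes the Aim 2 model.

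**Inputs for the check.** Predictors p = 7, all continuous (Section 12.0). Patients n = 14, 15 or 16 per model. The responder rate is not in the documents; I assume 50%, the case most favourable to the plan, and vary it. I assume one model per arm, with all predictors entered at once.

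**Probability of complete separation when no predictor matters.** For random 50/50 labels and predictors with no exact linear dependence, Cover's counting formula is exact:

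P = [sum over k = 0 to p of C(n−1, k)] / 2^(n−1)

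| n | p = 7 | p = 6 |
|---|---|---|
| 16 | 16384/32768 = 50.0% | 9949/32768 = 30.4% |
| 15 | 9908/16384 = 60.5% | 6476/16384 = 39.5% |
| 14 | 5812/8192 = 70.9% | 4096/8192 = 50.0% |

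The p = 6 column is there because breaths per minute appears neither among the measures in Section 4.0 nor among the procedures in Section 10.0.

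**At least one of the two arm models failing** (p = 7, 50% response): 1 − (1 − 0.500)² = 75% at 16 per arm, and 1 − (1 − 0.605)² = 84% at 15.

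**Other response rates** (p = 7, simulation with a linear-programming separability check, n = 16, 15, 14): about 64%, 74% and 81% at a 30% response; about 80%, 85% and 90% at an 80% response. Independent runs differ by two or three points.

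**Correlated predictors.** Correlation, for example between FVC and FEV1, does not help: simulation gave 60.7% at n = 15 and 51.3% at n = 16.

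**A real effect.** A log odds ratio of 1 per SD for MIP raises separation to 76% (n = 15) and 67% (n = 16).

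**Apparent fit under the null** (n = 15, p = 7, 50% response). Mean apparent AUC is 0.94 over all logistic fits, with separated fits counted as 1. Among non-separated fits it is 0.84.

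**Pooled alternative.** Two training arms, seven predictors, arm, arm-by-MIP and arm-by-MEP: with 15 per arm, separation is about 6% at a 50% response and about 46% at 80%; with 16 per arm, about 4% and 38%. Pooling with main effects and arm only gives about 0.3% to 1% at 50% and 20% to 24% at 80%, but yields no arm-specific profile. A fully interacted pooled model is the same as the two per-arm models.

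**One predictor at a time** (n = 15): 15/16384, or about 0.1%, at a 50% response; about 6% at 80%.

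**The case against.** **The model form is not stated.** Section 12.0 does not say one model per arm, nor that all seven predictors enter together; the sentence could introduce a candidate list. The interaction promised in Section 1.0 fits a pooled model, where separation is far less common at a 50% response. A reader might infer that the planned regression is bound to fail in half or more of trials. The documents do not support that without the per-arm, all-at-once assumption. It is the plainer reading, because the plan speaks of predicting improvement after each training, but it remains an assumption. Pooling also leaves separation at roughly 40% to 50% if most patients improve.

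**There may be only six predictors.** This stands. Without breaths per minute the probability falls below one half at 15 or 16 patients, although it remains large.

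**A reader might conclude that any profile from this trial is noise.** The null calculation does not show that; a real effect could be present. It shows that apparent discrimination would be high either way, so a profile could not be told from noise. Among null fits that did not separate, an overall likelihood-ratio test at 0.10 rejected only about 4% of the time, so a formal global test need not mislead there. The plan names no such test.

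**This is a pilot.** The documents describe proof-of-concept and feasibility work, and Section 2.0 makes clinical use conditional on validation. That limits the harm, and Aim 1 is untouched. It does not excuse a stated analysis that may have no estimates.

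**Conclusion.** The concern holds, conditionally. If Section 12.0 means one seven-predictor model per training arm, each model lacks finite estimates with probability 50% to 71% for 16 down to 14 patients, assuming no true effect and a 50% response. The probability is higher at other response rates or with a real effect. With six predictors it is 30.4% to 50.0%. A pooled model with two interaction terms does better, at about 6% for a 50% response with 15 per arm, but reaches about 46% at an 80% response. No responder rate is given, so these figures are a range and not a forecast. On every reading that yields arm-specific profiles from the seven predictors together, the model is too large for the data, and nothing in the plan handles non-convergence or optimism.

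**What to change.** In Section 12.0, Aim 2, replace the seven-predictor models with one prespecified test for each Section 1.0 hypothesis:

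- **Model.** Fit across arms, with treatment, the baseline measure and their interaction. Test baseline MIP for the IMST effect and baseline MEP for the EMST effect. A single-arm regression is not enough: without a comparator, a low MIP that predicts improvement could be merely prognostic, and the interaction question in Section 1.0 would go unanswered.
- **Outcome and method.** Use linear regression on the change in MPT and in GFI, or Firth-penalised logistic regression if the yes/no outcome is kept.
- **Other predictors.** Report them one at a time with confidence intervals. Label these, and any multivariable profile, exploratory, and state that no rule for selecting patients will be derived from this trial.
- **Breaths per minute.** State where and how it is measured, or delete it.

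The cost is wording only, with no extra patients or data. The multivariable profile is given up as a main result. Power remains modest: for 15 patients, a 50% response and alpha 0.10, a within-arm one-predictor Firth test has about 45% power for a log odds ratio of 1 per SD and about 30% for an odds ratio of 2. An interaction, being a difference between two slopes, will usually be estimated less precisely still. The protocol should say so, so that a null result is not read as evidence that baseline function is irrelevant.
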